9.7.3. Further evaluation

- Age, weight and height of the patients plus pregnancy and family anamnesis will be tabulated as well as gestation week, type of birth, placenta characteristics and Vitamin K prophylaxis.
- Complications during pregnancy and at birth will be listed.

CONFIDENTIAL

The information contained herein may not be used, disclosed, or published without the written consent of Biogen MA Inc.

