9.2.1. Selection Criteria

The patients will only be included in the study if they meet all of the following criteria:

Inclusion Criteria

1. Female patients of at least 18 years at time of informed consent
2. Diagnosed RRMS or CIS (CIS indication only applicable for interferon beta-1a)

CONFIDENTIAL

The information contained herein may not be used, disclosed, or published without the written consent of
Biogen MA Inc.

3. Exposure to either SC Peginterferon beta-1a therapy or an IM Interferon beta-1a therapy before or during pregnancy
4. Registered in the PSP of the MSSC and agreed in writing to the privacy policy of the registration form
5. Reported pregnancy data (pregnancy report and pregnancy outcome report) available at MSSC. Note: only pregnancy data (i.e. obtained until 15 October 2021) will be considered.

For the prospective part of the study:

6. Ability to understand the purpose of the study and provide signed and dated study-specific informed consent form (ICF)
7. Pregnancy outcome in the retrospectively collected data was a live birth

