9.4. Data Sources

9.4.1. Retrospective Data Capture

Main data source for the retrospective data capture is the MSSC database, i.e. the entered pregnancy report (to be completed as soon as pregnancy becomes known) and pregnancy outcomes report (to be completed after completion of pregnancy).

The following data is extracted from the MSSC database:

- Demographic data (age, height, weight)
- SC Peginterferon beta-1a or IM Interferon beta-1a use, including treatment duration, prior to, during and after pregnancy
- Concomitant medication prior to and during pregnancy
- Pregnancy outcome (live birth without defect, live birth with defects, ectopic pregnancy, spontaneous abortion, elective termination of pregnancy, preterm birth, stillbirth), including gestation week and description of abnormalities of the fetus, reason for termination, diagnostics, etc.
- Complications during pregnancy

CONFIDENTIAL

The information contained herein may not be used, disclosed, or published without the written consent of Biogen MA Inc.

- Type of delivery (vaginal delivery: spontaneous, induced, instrumentally supported; Caesarean section: elective, medically indicated), complications during delivery or reasons for an intervention
- Placenta normal/abnormal
- Data on newborn (sex, weight, height, head circumference, Apgar 1 minute, Apgar 5 minutes, Apgar 10 minutes)

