9.7. Data Analysis

This study is an observational study with focus on existing pregnancy reporting forms (retrospective part) and a patient's questionnaire which is completed at a single point of time (prospective part).

It will not be distinguished between the two treatments, i.e. the data will be pooled for analysis.

All documented data are analyzed by descriptive statistics, that is, no formal statistical hypothesis will be formulated, and no statistical tests will be carried out.

Categorical variables will be summarized descriptively by absolute frequencies and percentages. The denominator for all percentages will be the total number of pregnancies within the respective group, unless otherwise indicated. Percentages will be presented to one decimal place and will not be displayed for zero frequencies. A row denoted "Missing" will be included in all tabulations to clearly indicate the completeness of the collected data, i.e. missing data is included in the denominator of the percentages.

Continuous variables will be tabulated by descriptive statistics, i.e. the total number of pregnancies (n), number of pregnancies with missing values (Nmiss), mean, standard deviation, median, quartiles, minimum and maximum.

If sensible, free text entries will be transferred into appropriate encoding schemes to be analyzed in frequency tables. If appropriate, change of values during/after pregnancy to values before pregnancy will be calculated and analyzed using descriptive statistics or shift tables.

In case of missing or unknown data, no data imputation will be performed. For a complete presentation all obtained data will be listed.

A statistical analysis plan will be drafted and finalized before the end of the overall data collection to describe all analyses in more detail.

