9.7.2. Subgroup Analysis

Subgroup analyses will be performed with respect to patient's interferon beta-1a treatment history before during and after pregnancy. The primary endpoint will be evaluated in following subgroups:

- SC Peginterferon beta-1a or IM Interferon beta-1a was taken continuously before and during pregnancy
- SC Peginterferon beta-1a or IM Interferon beta-1a therapy was paused/stopped during pregnancy
- SC Peginterferon beta-1a or IM Interferon beta-1a therapy was started during pregnancy

The secondary endpoints will be evaluated in following subgroups:

- SC Peginterferon beta-1a or IM Interferon beta-1a was taken continuously before, during and after the pregnancy
- SC Peginterferon beta-1a or IM Interferon beta-1a therapy was started during pregnancy
- SC Peginterferon beta-1a or IM Interferon beta-1a therapy was paused during pregnancy and restarted promptly (within 1 week) after "life birth"
- SC Peginterferon beta-1a or IM Interferon beta-1a therapy was stopped during pregnancy and restarted more than a week after "life birth"
- SC Peginterferon beta-1a or IM Interferon beta-1a therapy was stopped during pregnancy and not restarted after "life birth"

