10.4. Participant Data Protection

Prior to any data collection under this protocol, participants must also provide all authorizations required by local law.

During the study, participants' age and gender will be collected. These data will be used in the analysis of the safety profile of the study treatment.

The participant will not be identified by name in the ePDFs, study-related forms, study reports, and related publications, and these reports will be used for research purposes only. Biogen, its partners and designee(s), ethics committees, and various government health agencies may inspect the records of this study. Every effort will be made to keep the participant's personal medical data confidential.

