9.2.3 Covariates and other characteristics? (e.g. age, sex, clinical and drug use history, co-morbidity, co-medications, lifestyle)				9.4.
9.3 Is a coding system described for:				

CONFIDENTIAL

The information contained herein may not be used, disclosed, or published without the written consent of Biogen MA Inc.

Section 9: Data sources	Yes	No	N/A	Section Number
9.3.1 Exposure? (e.g. WHO Drug Dictionary, Anatomical Therapeutic Chemical (ATC) Classification System)				9.7
9.3.2 Outcomes? (e.g. International Classification of Diseases (ICD), Medical Dictionary for Regulatory Activities (MedDRA))				CRF
9.3.3 Covariates and other characteristics?				9.7
9.4 Is a linkage method between data sources described? (e.g. based on a unique identifier or other)				

Comments:

Exposure of study drug does not need any coding, other medication and free text entries will be categorized in analysis programs and outcomes of children are already categorized in the standardized German pediatric check-up booklet.

Section 10: Analysis plan	Yes	No	N/A	Section Number
10.1 Are the statistical methods and the reason for their choice described?				9.5, 9.7
10.2 Is study size and/or statistical precision estimated?				9.5
10.3 Are descriptive analyses included?				9.7
10.4 Are stratified analyses included?				
10.5 Does the plan describe methods for analytic control of confounding?				
10.6 Does the plan describe methods for analytic control of outcome misclassification?				

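### The primary objective is worded as an effect of exposure, but outcomes are reported crude by treatment-history subgroup and maternal age is only tabulated, so age mix cannot be separated from exposure pattern

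*Protocol*

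**What the plan says.** - **Objective.** Section 8.2 frames the primary objective as the impact of exposure before and during pregnancy on pregnancy outcome.
- **Endpoints and analysis.** Section 9.1.1 defines the primary endpoints as numbers and proportions. Section 9.7 uses pregnancies as the denominator, pools the two products and is descriptive: "no formal statistical hypothesis will be formulated, and no statistical tests will be carried out".
- **Subgroups.** Section 9.7.2 splits results only by "interferon beta-1a treatment history before during and after pregnancy". For the primary endpoint there are three groups: continuous use, paused or stopped during pregnancy, and started during pregnancy.
- **Age.** Section 9.4.1 extracts "Demographic data (age, height, weight") for the retrospective part. Section 9.7.3 states its use: "Age, weight and height of the patients plus pregnancy and family anamnesis will be tabulated".
- **Confounding.** In Annex 2, item 10.5 ("Does the plan describe methods for analytic control of confounding"), item 10.4 (stratified analyses) and item 7.1 (measuring confounding) are all answered No. Item 12.1.3, on residual confounding, is answered Yes with a pointer to 9.9.
- **Limitations.** Section 9.9 names the lack of an internal reference therapy, and missing or implausible values. It does not mention age or confounding.

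**The concern.** The study does not assign treatment patterns. Whether a woman continued, stopped or started during pregnancy was decided in ordinary care, so nothing makes the three groups alike in age. If the risk of pregnancy loss varies with maternal age, two groups can show different crude proportions with no difference in the effect of exposure. A reader who takes the objective at its word would read such a difference as an effect of the exposure pattern.

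A single overall age table does not let the reader check this. It shows neither how age is distributed across the subgroups nor how the outcomes vary with age. The variable needed is already extracted, so the gap lies in the planned presentation and not in data collection.

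**Working it through.** **The plan's own figure.** The protocol derives no figure on this point. Its one derived number reproduces: 368 live births × 0.80 = 294.4, against about 290 questionnaires (9.5). It does not bear on age.

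**Is the choice fixed or left open?** Section 9.7 defers detail to a SAP. The checklist, however, answers No to stratification and to control of confounding, and 9.7.2 lists subgroups by treatment history only. A SAP that merely adds detail would not change this; it would have to reverse those answers.

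**Is the checklist consistent with the text?**

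| Checklist item | Answer | Text |
|---|---|---|
| 10.4 stratified analyses | No | 9.7.2 plans treatment-history subgroups |
| 12.1.3 residual confounding discussed | Yes, in 9.9 | 9.9 does not mention it |

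**One age per woman or per pregnancy?** Inputs from 9.5, reading each report pair as one pregnancy:
- Pregnancies: 202 + 245 = 447.
- Women: 184 + 199 = 383.
- Further pregnancies in women already counted: 447 − 383 = 64 (more if any woman appears under both products).

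One age per woman therefore cannot be the age at each pregnancy.

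**How large could an age effect be?** The protocol gives no age distribution and no age-specific risks, so everything here is an assumption except the 10.7% spontaneous-abortion proportion, which is the registry figure in 7.1.2. Let *s* = 0.30 be the overall share of older women, *RR* the ratio of loss risk (older to younger), and *d* the difference in older share between two subgroups.

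- Risk in the younger stratum: r₀ = 0.107 / (1 − s + s·RR)
- Crude difference due to age alone: r₀ · (RR − 1) · d

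| RR | r₀ | d = 0.10 | d = 0.30 |
|---|---|---|---|
| 1.0 | 10.7% | 0 points | 0 points |
| 1.5 | 0.107/1.15 = 9.3% | 0.5 | 1.4 |
| 2.0 | 0.107/1.30 = 8.2% | 0.8 | 2.5 |
| 2.5 | 0.107/1.45 = 7.4% | 1.1 | 3.3 |

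**Against sampling error.** At the registry proportion, 0.107 × 447 ≈ 48 losses, with an exact (Clopper-Pearson) 95% interval of 8.0% to 14.0% and a half-width of 3 points. The assumed age shift is of that order or smaller. Intervals for single subgroups would be wider; their sizes are not given.

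**Rare outcomes.** At the registry's 1.8% for congenital anomalies, 0.018 × 368 ≈ 7 cases (exact 95% interval 0.8% to 3.9%). Spread over three subgroups and two age bands, that is about one case per cell.

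**The case against.** The strongest reply is that the study is openly descriptive and non-comparative, runs no tests and specifies no formal contrast between subgroups. A crude proportion is then not wrong in itself, and variable definitions and table layouts are ordinary SAP content. Much of this stands. It does not remove the mismatch with an objective worded as impact, nor the fact that the subgroups are set out by exposure pattern, which invites the comparison.

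The size is also wholly assumed and does not exceed the sampling uncertainty of the whole cohort by any useful margin. That stands too, and it limits how much weight the point can carry.

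Three stronger readings are tempting, and the documents do not support them:
- **That 10.4 is contradicted.** It says of age and gender that "These data will be used in the analysis of the safety profile of the study treatment". This is a general sentence in a data-protection section. Tabulation is a weak use of age, but it is a use.
- **That age is taken at consent or at extraction.** Consent age appears only as an eligibility threshold ("Female patients of at least 18 years at time of informed consent", 9.2.1), and the retrospective part has no separate consent. The source in 9.4.1 includes the "pregnancy report (to be completed as soon as pregnancy becomes known"), so an age close to early pregnancy probably exists. The protocol simply does not say which age is used.
- **That results should be age-standardised against outside figures.** The registry percentages in 7.1.2 are background. No such comparison is planned, and the age structure it would need is not in the protocol.

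**Conclusion.** The point holds as a mismatch between the objective and the analysis. The protocol asks about the impact of exposure, reports crude proportions by treatment patterns that the study did not assign, and states that it neither stratifies nor controls for confounding. Age mix may therefore explain part of any difference between the treatment-history subgroups, and the planned tables would not show whether it does.

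The documents do not show that an age effect exists, or its direction or size. The range of about 0 to 3 percentage points in the loss proportion rests on an assumed 30% share of older women, risk ratios of 1.0 to 2.5 and share differences of 10 to 30 points. This is a worthwhile, cheap improvement and not a flaw that invalidates the primary analysis. The two checklist mismatches (items 10.4 and 12.1.3) need no assumption.

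**What to change.** - **9.7:** state that age means age at the start of each pregnancy, derived per pregnancy.
- **9.7.2:** show the age distribution beside each treatment-history subgroup. Present the common primary outcomes, such as spontaneous abortion and live birth, by age band, for example under 35 and 35 or over. Leave rare outcomes unbanded, or list them.
- **9.9:** name age and other confounding as a limitation on reading subgroup differences as effects of exposure. This also makes checklist item 12.1.3 true.
- **Annex 2:** correct item 10.4, since 9.7.2 plans subgroup analyses.

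The cost is one derived variable and a few more tables from data already to be extracted. The drawback is thin cells: with about 7 anomalies expected at the registry proportion, banding them would tell the reader little.

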9.7.4. Interim Analyses

No interim analysis is planned for this study.

9.8. Quality Control

The study will be conducted and reported in accordance with the “Guideline on good pharmacovigilance practices (GVP) Module VIII - Post-authorisation safety studies”.

Data management and quality assurance for the study are in accordance with the German document „Gemeinsame Bekanntmachung des Bundesinstituts für Arzneimittel und Medizinprodukte (BfArM) und des Paul-Ehrlich-Instituts (PEI) zur Anzeige von Anwendungsbeobachtungen nach §67 Absatz 6 Arzneimittelgesetz und zur Anzeige von nichtinterventionellen Unbedenklichkeitsprüfungen nach §63f und g Arzneimittelgesetz“ in the final version of December 20th, 2019.

Retrospective data are automatically checked for plausibility, completeness and mandatory information by programmed edit checks during the data entry by the MSSC in their database. Pregnancy data is further checked for consistency and plausibility by a trained medical documentation officer before being sent to Biogen Pharmacovigilance department. By using the ePDF for the patient questionnaire, data are entered by the MSSC in a standardized way and simple checks are implemented. The prospective and retrospective data of lactation and Interferon therapy will be manually cross-checked for consistency by MSSC.

MSSC checks also the patient questionnaires (ePDF) manually for potential adverse and other safety events and reports the events to the Sponsors Pharmacovigilance as per section 11.3.

For quality control purposes, random samples of all MSSC contacts are checked for compliance with Good Documentation Practice and missed adverse events on a daily basis. Pharmacovigilance relevant information is further checked for consistency and integrity by a trained medical documentation officer and is submitted directly to Biogen or to appointed third parties for pharmacovigilance services.

Due to the non-interventional character of the study, missing values and/or implausibility may persist and will be accepted.

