9.4.2. Prospective Data Capture

If the pregnancy report or the pregnancy outcome report is incomplete, i.e. the data above was not collected, the open questions will be addressed during a telephone interview performed by the MSSC and the new information will be entered into the MSSC database. No further assessments other than completion of the questionnaire are applicable for patients participating in the prospective study part. The patient questionnaire is completed at a single point of time during the telephone interview performed by the MSSC.

The patient questionnaire covers the following questions:

- Abnormalities diagnosed during pediatric check-ups under statutory programs as reported in the standardized German pediatric check-up booklet “Kinderuntersuchungsheft” (data on check-ups 1-8 will be collected covering the first 46-48 months of life)
- Pregnancy and family anamnesis
- Vitamin K prophylaxis
- Body weight, height, head circumference of the child as documented for check-ups 2-8.
- Lactation:
 - Exclusive breastfeeding and duration (1st week, 1 month, 2 months, 3 months, 5 months, 6 months, 7-9 months, 10-12 months, > 12 months) of breastfeeding
 - Supplemental feedings (starting month after birth)
- Other MS therapies (non-interferon beta-1a DMTs) during or after pregnancy and start relative to birth (during pregnancy, < 1 week after birth, after 1 week, after 2 weeks, after 3 weeks, after 4 weeks, after 6 weeks, after 2 months, after 3 months, after 4 months, after 5 months, after 6 months, after 7 months, after 8 months, after 9 months, after 10 months, after 1 months, after 12 months or later))
- Frequency of MS relapses in the year before pregnancy
- Time (1st trimester, 2nd trimester, 3rd trimester) and frequency of MS relapses during pregnancy

CONFIDENTIAL

The information contained herein may not be used, disclosed, or published without the written consent of Biogen MA Inc.

- Time (< 1st month, 1st – 2nd month, 3rd - 4th month, 5th - 6th month, 7th - 8th month, 9th - 10th month, 11th - 12th month, 13th - 14th month, 15th - 16th month, 17th - 18th month, > 18th months) and frequency of MS relapses after pregnancy/birth
- EDSS before, during and after pregnancy

The information collected by the MSSC will be stored in a secure database.

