11.3. Monitoring and Recording Events

11.3.1. Non-Serious and Serious Adverse Events

Any pregnancies and any AEs related to the pregnancies that are analysed as part of this study have been collected and reported to Biogen in the frame of routine pharmacovigilance activities in the past. Non-serious (NSAEs) and serious (SAE) events related to study endpoints about child development and maternal MS relapses (Refer to Section 9.1 for details) will be collected prospectively from the participants in a phone interview by the MSSC and recorded as part of this study. The interview follows a predetermined structure with standardized questions. In addition, the interview may generate updates to the previously provided pregnancy data. This data will be recorded and submitted within the study.

Any other safety events (i.e. AE, pregnancies, medication errors etc.) reported spontaneously by the participants by phone will not be documented as an event within this study but will be documented and reported as spontaneous events according to standard local postmarketing channels. **Deaths**

Death is an outcome of an event. The event that resulted in death should be recorded and reported as an SAE. Biogen or designee will make every effort to obtain death certificates and autopsy reports from the reporter. The term death is reported as an SAE only if the cause of death is not known and cannot be determined.

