11.5. Biogen Responsibilities

Biogen or designee's responsibilities include the following:

- Review all AEs to determine seriousness and fulfillment of collection criteria defined in Section 11.2.
- Monitor and record all SAEs and NSAEs as defined in Section 11.1, regardless of the relationship to IM Interferon beta-1a or SC Peginterferon beta-1a
- Determine the relationship of each SAE and NSAEs to IM Interferon beta-1a or SC Peginterferon beta-1a as per Biogen standard procedure
- Record all spontaneously reported AE or pregnancies according to spontaneous reporting process
- Pursue AE follow-up information as per Biogen standard procedure
- Determine the expectedness of all AEs
- Notify all appropriate regulatory authorities as required by local law, within required time frames.

CONFIDENTIAL

The information contained herein may not be used, disclosed, or published without the written consent of Biogen MA Inc.

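### The named cross-check of prospective against retrospective data omits congenital-anomaly status, so a complete outcome report is not systematically compared with congenital findings from the child's check-ups

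*Protocol*

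**What the plan says.** Section 9.1.1 makes live births with and without congenital anomalies part of the primary endpoint. Section 9.4.1 takes this status from the pregnancy outcome report in the service-center database: "Pregnancy outcome (live birth without defect, live birth with defects" are two of its codes.

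Section 9.4.2 collects a second set of findings on the same children by telephone: "Abnormalities diagnosed during pediatric check-ups under statutory programs as reported in the standardized German pediatric check-up booklet". These cover check-ups 1-8 and feed a secondary endpoint in 9.1.2. The same section has the interview address outcome-report items where the report is incomplete.

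Section 9.8 describes these checks:
- Before the interview, on the retrospective data: programmed edit checks, and then "Pregnancy data is further checked for consistency and plausibility by a trained medical documentation officer before being sent to Biogen Pharmacovigilance department".
- Between the two sources: "The prospective and retrospective data of lactation and Interferon therapy will be manually cross-checked for consistency by MSSC".
- On the questionnaires: "MSSC checks also the patient questionnaires (ePDF) manually for potential adverse and other safety events and reports the events to the Sponsors Pharmacovigilance".

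Section 11.3.1 adds: "In addition, the interview may generate updates to the previously provided pregnancy data. This data will be recorded and submitted within the study". Section 9.6 sends completed questionnaires for analysis and for updating the service-center database.

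**The concern.** The anomaly proportion is a central safety figure of the study. The study collects a second account of the same children that could show whether the outcome report missed congenital findings, yet the protocol does not direct anyone to compare the two. The trigger for returning to an outcome item is a gap in the report, so an entry that is complete but wrong is not covered. If it stands, the child is counted as free of anomalies in the primary table, which lowers the proportion in the reassuring direction. The final report could then carry a congenital finding in the secondary table for a child whom the primary table counts as unaffected, with nothing to flag it.

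**Working it through.** **1. What is cross-checked against what can be cross-checked.** In the Annex 3 flowchart, breastfeeding is marked for the questionnaire only and interferon history for the database only. Among the rows after enrollment, only the data on the newborn child are marked in both columns. The named cross-check therefore covers two items with one listed source each. It leaves out the row with two sources, and it leaves out anomaly status, on which the outcome report and the booklet overlap.

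**2. Whether the overlap is real.** Annex 3 places check-up 1 after birth and check-up 2 at 3-10 days. The early examinations include skeleton, hip joint and genitals, and a pulse oximetry screen linked to congenital heart defects. These are congenital findings in the period that the outcome report describes.

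**3. What reopens an outcome entry.** Section 9.4.2: an incomplete report. Section 9.6: missing data completed in the form. Section 11.3.1: the interview may produce updates. None of these names disagreement between sources as a trigger, and none says which source prevails. Section 9.8 ends by accepting that implausible values may persist. In Annex 2, items 6.3 (validity of outcome measurement) and 10.6 (control of outcome misclassification) are both answered No.

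**4. The plan's own count.** Section 9.5 gives 368 live-birth pregnancies and an 80% return rate: 0.80 x 368 = 294.4, which agrees with the stated figure of about 290. At 290, 290/368 = 79% can be compared, and 368 - 290 = 78 (21%) cannot. All reports: 202 + 245 = 447.

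**5. Expected anomalies.** Section 7.1.2 cites 1.8% in the European registry and 2.1% to 4.1% in the general population. Expected number = prevalence x live births:
- 0.018 x 368 = 6.6
- 0.021 x 368 = 7.7
- 0.041 x 368 = 15.1

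**6. Shift per reclassified child.** 1/368 = 0.27 percentage points. With all pregnancies as denominator, 1/447 = 0.22 points. As an example, 7/368 = 1.9% and 8/368 = 2.2%, so one child moves the point estimate across the lower end of the cited population range. Going from 1.8% to 4.1% takes 15.1 - 6.6 = about 8.5 children. The exact 95% interval for 7/368 is 0.8% to 3.9%, so one child does not change the statistical reading. A few children do change a figure built on about 7 to 15 events.

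**The case against.** The strongest reply is that a route already exists. Every questionnaire is screened for safety events, section 11.1.2 counts a congenital anomaly as serious, section 11.3.1 allows the interview to update pregnancy data, and section 9.6 feeds the forms into the analysis. This stands against the stronger claim a reader might infer, that anomaly status is never compared with anything or that a wrong code is bound to remain. The documents do not support that. They support only that the route is permissive, with no systematic comparison and no precedence rule.

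A reader might also infer that a child listed as without anomaly in one table and abnormal in another shows the report contradicting itself. In general it does not. Check-ups run to 48 months and include allergies, overweight, language and behaviour. Only a congenital finding absent from the outcome report is discordant.

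A third tempting inference is that the sponsor's safety file is an independent check. Section 11.3.1 says the pregnancies "have been collected and reported to Biogen in the frame of routine pharmacovigilance activities in the past", so the file starts from the same reports. Section 11.5 promises to "Pursue AE follow-up information as per Biogen standard procedure", but the documents do not show whether that follow-up holds anything the database lacks. The booklet is not fully independent either, since its content reaches the study through the mother.

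The named check may also have a sensible purpose, because breastfeeding under therapy combines lactation and interferon data. That explains why those items are included. It does not explain why anomaly status is left out.

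Finally, tables and listings can be left to the SAP, which was not available here. That holds for the tabulation. The scope of the service-center check is fixed in the protocol, however, and the interview takes place once. An analysis plan cannot by itself add a clarification with the mother.

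**Conclusion.** The point holds in a limited form. The protocol fixes a cross-check that leaves out a primary endpoint for which a second account is being collected, and it ties reopening of that endpoint to missing data. A congenital anomaly missed in a complete outcome report can therefore stay out of the primary proportion. The effect of a missed anomaly is downward. Its size is unknown, because the documents give no figure for how completely outcome reports capture anomalies. What can be stated is the sensitivity: 0.27 points per child on 368 live births, or 0.22 on 447 pregnancies, against an expected 7 to 15 affected children. This assumes that the cited 1.8% to 4.1% applies to this population and that the mid-July 2020 counts are close to the final ones. The change is worth making because it is cheap and can reveal or remove a bias in a main safety figure. It does not show that the figure will be wrong.

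**What to change.** - **Section 9.8:** add congenital-anomaly status and newborn measurements to the service-center cross-check, and have discrepancies clarified with the mother during the interview. Birth values and check-up 2 values are taken days apart, so the measurements should be compared for plausibility and not for equality.
- **Analysis, for interviewed live births:** cross-tabulate outcome-report anomaly status against congenital abnormality documented at check-ups 1-8. Give the anomaly proportion from each source in that same group, and list the discordant children. Keep the outcome-report figure as primary. Define congenital beforehand, so that acquired and developmental findings do not enter the table. The table would also show anomalies reported at birth that the booklet does not confirm.
- **Optional:** a listing against the sponsor's safety cases, useful only where follow-up arrived after the service-center report.

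The cost is a little extra data-management work, one table and one listing. The comparison covers only the roughly 80% of live births with an interview, and the reported anomaly proportion may turn out slightly higher.
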